### 6.1.3 Eligibility of matched historical controls

Historical controls with COVID-19 (confirmed either via PCR or radiologically) will be selected on the basis of the matching criteria stated in section 10.4.2 only. Historical controls must be aged 16 years or over.

### 6.1.4 Trial participant exclusion criteria – Cohort 2

1. Females who are pregnant
2. Known allergies to the IMP or excipients of IMP
3. Fibrinogen < 1.5 g/L at time of screening
4. Patients considered inappropriate for active treatment (e.g. being considered for palliative care)
5. Patients who in the opinion of the investigator are not suitable

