# 6 Selection of Participants

## 6.1 Eligibility of trial participants

### 6.1.1 Trial participant inclusion criteria – Cohort 1 and Cohort 2

All patients must meet the following criteria (ward or ICU based):

1. Patients with COVID-19 (confirmed by PCR or radiologically)
2.  $\geq 16$  years
3. Willing and able to provide written informed consent or where patient doesn't have capacity, consent obtained from a legal representative if available
4. Patients on mechanical ventilation must meet the following criteria:
  - a.  $\text{PaO}_2/\text{FiO}_2$  of  $\leq 300$
  - b. Intubated  $> 6$  hrs
5. Patients not intubated must meet the following criteria:
  - a.  $\text{PaO}_2/\text{FiO}_2 \leq 300$  or equivalent imputed by non-linear calculation from  $\text{SpO}_2/\text{FiO}_2$  (see look-up table in appendices)
  - b. In-patient  $> 6$  hours and being actively treated
  - c. On support with non-invasive ventilation OR continuous positive airway pressure (CPAP) OR high flow OR standard oxygen therapy

### 6.1.2 Trial participant exclusion criteria – Cohort 1

None of the following criteria must apply:

1. Females who are pregnant
2. Concurrent involvement in another experimental investigational medicinal product
3. Known allergies to the IMP or excipients of IMP
4. A pre-existing bleeding disorder (e.g. severe haemophilia) with no definitive treatment
5. Pre-existing severe cardiopulmonary disease (e.g. incurable lung cancer, severe chronic obstructive lung disease, cardiomyopathy, heart failure or impaired contractility <estimated 40% LVEF or RVEF)
6. Fibrinogen < 2.0 g/L at time of screening
7. Patients considered inappropriate for active treatment ( e.g. being considered for palliative care)
8. Patients with active bleeding in the preceding 7 days
9. Patients who in the opinion of the investigator are not suitable

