## **7.2 Registration Procedures**

Participant registration will be undertaken by the coordinating trial team at site on a trial specific registration form.

Participants are considered to be enrolled into the trial following: consent, pre-treatment assessments (see section 7.1), confirmation of eligibility, completion of the registration process, allocation of the participant trial number.

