### **10.6.1 Summary of baseline data and flow of participants**

All pre-treatment assessments data in the protocol will be listed and all relevant data will be tabulated for each group separately.

For patients treated with rtPA + SOC, the last available value prior to the first administration of IMP will be considered the baseline value.

For patients receiving SOC only (historical controls), the last available value prior to enrolment, as defined in section 8.2, will be considered the baseline value.

All data necessary to produce a consort flow diagram (<http://www.consort-statement.org/>) will be summarised: the number of patients in each group that were enrolled, assessed for eligibility, excluded (with reasons listed), assigned to a group, treated with rtPA + SOC, followed up, discontinued (with reasons such as lost to follow-up, withdrawn, or death), and number of patients analysed in each group, and where applicable excluded from analyses (with reasons).

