### **10.6.2 Primary outcome analysis**

The PaO2/FiO2 ratio measured over time will be described for each group. The change from baseline in the PaO2/FiO2 ratio will be summarised at each post baseline timepoint. Plots will be used, where appropriate, to show the PaO2/FiO2 summarised for patients over time.

PaO2/FiO2 will be a calculated field on the trial database derived from the fields for PaO2 and FiO2. For cohort 2 data will be extracted once a day coinciding with the worst PF ratio. As PF ratio is the primary endpoint, in addition to the worst PF ratio, up to a maximum of 6 data points spread across 24 hrs that represents patients clinical status will be extracted. Details of further data derivation and analyses will be described in the SAP.

All patient data will be used, regardless of any intercurrent events that may have occurred after enrolment:

- Data from patients recruited into the rtPA + SOC group will be summarised whether or not patients have received all planned doses of the IMP.
- Any change in requirement for oxygenation and ventilation support will be summarised and described
- Changes in PaO2/FiO2 ratio over time will be described and interpreted taking into consideration that a patient's condition may have changed and led to their ventilation type changed post enrolment. If data allows, additional descriptions of the PaO2/FiO2 ratio over time may be performed in each subgroup of patients experiencing such changes (e.g. IMV to NIV, or vice versa).

The incidence and severity of bleeding events will be summarised in each group, and the change in fibrinogen levels will also be summarised at each post-baseline timepoint.

For cohort 1, subject to the final sample size and data quality, outcomes will also be compared between the SOC only group and intervention (rtPA + SOC) group using appropriate regression methods to make adjustment for baseline characteristics. Appropriate data transformations required for model assumptions will be considered if necessary.

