6.2 Summary of baseline characteristics

All baseline covariates and baseline valued of the outcomes will be summarised using descriptive statistics. For patients treated with rtPA + SOC, the last available value prior to the first administration of IMP will be considered the baseline value. For historical controls receiving SOC only, the last available value prior to enrolment, as defined in section 8.2, will be considered the baseline value. Categorical variables shall be reported as frequencies and percentages. Reports of continuous variables shall include mean or median and standard deviation or interquartile range (IQR) as appropriate, as well as minimum and maximum values.

Summary measures for the baseline characteristics will be presented both overall and by group. We will compare baseline characteristics visually to assess whether balance has been achieved. No significance testing will be used. The number of missing observations will be reported.

A CONSORT flow chart will be provided (Schulz et al., 2010). This will include the number of eligible participants, number of participants agreeing to enter the trial, then by intervention arm: the number of patients in each group that were enrolled, assessed for eligibility, excluded (with reasons listed), assigned to a group, treated with rtPA, followed up, discontinued (with reasons such as lost to follow-up, withdrawn, or death), and number of patients analysed in each group, and where applicable excluded from analyses (with reasons).

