6.3 Analysis of primary outcome

The primary outcome for efficacy is oxygenation, measured using the PaO₂/FiO₂ ratio over time. The distributions of the primary outcomes will be summarised, by group, over time. Change in PaO₂/FiO₂ ratio from baseline will be checked visually using means & SE plots. If necessary, appropriate transformations of the data will be performed (e.g., using the natural logarithm).

Subject to the final sample size and data quality, PaO₂/FiO₂ ratio will also be compared between the SOC group (historical controls) and rtPA group using appropriate regression modelling, controlling for baseline oxygenation ratio:

$$OXY_i = \beta_0 + \beta_1 \cdot T_i + \beta_2 \cdot OXY0_i + \varepsilon_i,$$

where the i subscript denotes the i^{th} patient and

- OXY_i = PaO₂/FiO₂ ratio (oxygenation) at the end of treatment;
- T_i = group indicator (= 1 if patient is in the rtPA group, = 0 otherwise);
- $OXY0_i$ = PaO₂/FiO₂ ratio (oxygenation) at baseline;
- $\varepsilon_i \sim N(0, \sigma^2)$ = Normally distributed error term.

The estimate of the parameter β_1 and associated 95% confidence interval shall be reported, as well as a p-value pertaining to the hypothesis test of

$$H_0: \beta_1 = 0 \text{ versus } H_1: \beta_1 \neq 0.$$

Similarly, the use of models using oxygenation at other meaningful timepoints as outcome measure will be evaluated. Owing to a limited sample size, models shall not adjust for other baseline characteristics. Fitted models shall be checked, where appropriate, to ensure that modelling assumptions have been satisfied. Appropriate transformations of outcomes or other suitable approaches (e.g., robust or non-parametric methods) shall be explored if model assumptions are not satisfied.

For treatment safety, the incidence and severity (either major or minor) of bleeding events will be summarised with frequencies and percentages in each group. Fibrinogen levels will also be summarised graphically using plots of the mean, by group, over time. Finally, the number and nature of serious adverse events (SAEs) will be summarised. These events are defined in section 8 of the protocol.

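### Cohort 1 historical controls are chosen on the matching list alone, so the prognostic exclusions applied to rtPA patients are not applied to them, and no planned analysis shows how far this moves the comparison

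*Protocol*

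**What the plan says.** **Who may be a control.** Protocol 6.1.3 states that controls "will be selected on the basis of the matching criteria stated in section 10.4.2 only". It adds only COVID-19 confirmation and a minimum age of 16. The list in 10.4.2 is support type, severity by P/F ratio, gender, age and ethnicity. The same section removes patients who died soon after admission.

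**Who may receive rtPA in Cohort 1.** Protocol 6.1.2 has nine exclusions. Those with a plausible link to outcome are severe cardiopulmonary disease, "Patients considered inappropriate for active treatment", and concurrent use of another investigational product. None is on the matching list.

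**The comparison.** SAP 6.3 regresses end-of-treatment P/F on group and baseline P/F. It opens with "Subject to the final sample size and data quality" and adds: "Owing to a limited sample size, models shall not adjust for other baseline characteristics". Protocol 10.6.2 is wider, referring to a comparison "using appropriate regression methods to make adjustment for baseline characteristics".

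**Sensitivity analysis.** Protocol 10.6.4 leaves this to the SAPs. The SAP contents page lists a section 6.5 for it with a broken bookmark, but the body passes from 6.4 to 7.

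**Control baseline.** Protocol 10.6.1 takes "the last available value prior to enrolment, as defined in section 8.2", and SAP 6.2 does the same: "For historical controls receiving SOC only, the last available value prior to enrolment, as defined in section 8.2". Protocol 8.2 is about recording adverse events, and the SAP has no section 8.2.

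**The concern.** The two groups differ in eligibility by rule, not by chance. A control with end-stage lung disease, or one for whom palliative care was being considered, could be matched to an rtPA patient who could not have entered with that condition. Matching on support type and P/F covers part of this, but 10.4.2 gives no tolerance for P/F, and P/F does not stand in for comorbidity or treatment intent.

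Adjustment for baseline P/F would not remove such a difference. The visual baseline comparison in SAP 6.2 may reveal it, but would not show what it does to the estimate. The estimate has a use: protocol 2.5 says controls were recruited so that a phase 3 sample size could be calculated, and under 12.2 the DMC advises on an RCT from the final results.

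**Working it through.** **1. Counts.** Protocol 4.1 gives 9 rtPA patients (6 on IMV, 3 on non-invasive support) and two controls each: 2 × 9 = 18, as stated. By support type that implies 2 × 6 = 12 IMV and 2 × 3 = 6 non-invasive controls. No power, SD or effect size is stated, so there is no sample size calculation to reproduce.

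**2. Precision.** In residual-SD units, with an outcome available for all 27 patients:
- SE = √(1/9 + 1/18) = 0.408
- residual df = 27 − 3 = 24, t(0.975) = 2.064
- 95% half-width = 2.064 × 0.408 = 0.84 SD

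**3. Illustrative shift.** The documents do not give the number of ineligible controls (k) or how much worse they end (d, in SD). Shift toward rtPA = (k/18) × d.

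| k (assumed) | d (assumed) | Shift (SD) | Share of half-width |
|---|---|---|---|
| 2 | 0.5 | 0.056 | 7% |
| 2 | 1.0 | 0.111 | 13% |
| 4 | 0.5 | 0.111 | 13% |
| 4 | 1.0 | 0.222 | 26% |

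**4. Direction.** If the ineligible controls did better, for instance because another investigational product helped them, the sign reverses: d = −0.5 gives −0.056 (k = 2) or −0.111 (k = 4). Mixtures can go either way. Assume frail controls end 75 mmHg lower and controls on another product 50 mmHg higher:
- 3 frail, 1 on another product: (3 × 75 − 1 × 50)/18 = +9.7 mmHg toward rtPA
- 1 and 3: (75 − 150)/18 = −4.2 mmHg
- 2 and 3: (150 − 150)/18 = 0

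Two further rules can also work against rtPA. Early deaths are removed from controls only (10.4.2), and SAP 6.1 makes no adjustment for missing data, so a control who dies before the outcome time may contribute no P/F value.

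**5. Can eligibility be checked as written?** The fibrinogen and recent-bleeding exclusions need a reference time. For controls this is enrolment, with a pointer to a section on another subject. Protocol 7.2 does define enrolment ("Participants are considered to be enrolled into the trial following: consent, pre-treatment assessments"), but 6.4 says controls are not asked for consent. End of treatment, the outcome time in SAP 6.3, is also undefined for a patient who was never treated.

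**6. Cost of a restricted run.**
- 16 controls: SE = √(1/9 + 1/16) = 0.417, up 2%; half-width 0.86 SD (22 df)
- 14 controls: SE = √(1/9 + 1/14) = 0.427, up 5%; half-width 0.89 SD (20 df)

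**The case against.** The rule is stated openly, and the plan handles part of its consequence. Protocol 7.5.2 collects history, medication, blood results and other findings that may explain P/F change in controls. SAP 6.2 compares baseline by group, and SAP 2.1 allows further documented analyses. Several 6.1.2 items are drug-safety screens with no documented link to P/F. Support type is matched first, and palliative decisions are plausibly rare among the 12 or so IMV controls. All results are labelled hypothesis-generating. This stands, and it limits the weight of the point. It does not fill the gap: nothing planned counts the ineligible controls or shows the estimate without them, and the SAP section where this would sit is absent.

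Four stronger readings are tempting but not supported:
- *The comparison is biased in favour of rtPA.* The documents give neither the number of ineligible controls nor their outcomes, and some rules push the other way.
- *The false-positive rate is seriously inflated.* In the worst case tabulated (k = 4, d = 1.0), simulation gives about 6.6 to 7.1% against a nominal 5%, because such a subgroup also raises the residual variance. That rests on assumed inputs, in an analysis declared descriptive.
- *Phase 3 would be mis-sized because of this.* At an SE of 0.408 SD, sampling error swamps a shift of this size in any sample size derived from the estimate.
- *Controls were in other drug trials.* Protocol 4.1 mentions other interventional studies only when explaining why patients were not randomised. The selection rule permits such controls, but no passage says there were any.

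**Conclusion.** The point holds as a gap in the plan. The Cohort 1 groups are defined by different eligibility rules, the SAP model adjusts for baseline P/F alone, and no analysis is specified to show the consequence. Size and net direction cannot be determined from the documents. The illustrative shift of 0.06 to 0.22 SD is 7 to 26% of the confidence half-width, so sampling error is the larger problem. That range assumes 2 to 4 ineligible controls ending 0.5 to 1.0 SD worse, a residual SD common to both groups, and an outcome for every control at a time the SAP has yet to define. Severity is minor to moderate: the analysis is descriptive, and the regression depends on final sample size and data quality.

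**What to change.** 1. In protocol 10.6.1 and SAP 6.2, replace the section 8.2 reference for controls with an index time, such as the time of the record used for matching. In SAP 6.3, define the control timepoint that corresponds to end of treatment, such as the same elapsed time from index as in the matched rtPA patient.
2. From the 7.5.2 data and a short notes check, tabulate how many of the 18 controls would fail each 6.1.1 or 6.1.2 criterion that records can verify. Consent, pregnancy testing, allergy to the product and investigator opinion cannot be checked this way. Use only information up to the index time, because 7.5.2 data run for 28 days from admission.
3. Keep all 18 controls in the main comparison. As the missing SAP sensitivity analysis, add one run without the flagged controls, and report both estimates to the DMC.
4. Reconcile the early-death rule for controls, which is 48 hours in protocol 10.4.2 and 2 to 3 days in SAP section 4.

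The cost is some wording, one table, one model run and a check of 18 records. History, medication and fibrinogen are already collected; bleeding, ejection fraction and palliative decisions are not named in 7.5.2 and need the notes. The restricted run has an SE about 2 to 5% larger if 2 to 4 controls are removed, and some patients lose the 2:1 ratio. It does not address other historical-control bias, such as the unlimited look-back in protocol 6.4.

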## 6.2 Recruitment

Patients will be identified by the clinical team involved in the patient's routine care in either wards or ICU. As described in section 6.3 patients will either go through the consenting process themselves or, if they do not have the capacity, consent will be obtained from their legal representative.

All trial related activities will ideally be carried out by site staff delegated to the trial. As nebulisation will need to be regularly undertaken over 14 days, trained nurses who are used to nebulisation will be permitted to undertake this procedure, with two nurses double checking the dilution and amount of rtPA being reconstituted.

The only procedures that may be performed in advance of written informed consent being taken are those that would have been performed on all participants in the same situation as routine clinical practice.

Participant recruitment at a site will only commence when the trial has been issued with the 'Open to Recruitment' letter by the sponsor.

### 6.3 Informed consent procedure

It is the responsibility of the Investigator, or a person delegated by the Investigator to obtain written informed consent from each participant prior to participation in the trial, following adequate explanation of the aims, methods, anticipated benefits and potential hazards of the trial.

The person taking consent will be GCP-trained, suitably qualified and experienced, and will have been delegated this duty by the CI/ PI on the Staff Signature and Delegation of Tasks.

**“Adequate time”** must be given for consideration by the participant/legal representative before taking part. Consent will ideally be sought at least 24 hours after being given the study documentation.

However, given the need to urgently begin treatment in many of these patients, it may not be justifiable to seek consent at least 24 hours after providing the study documentation, as the patient’s condition may deteriorate over this time. In these instances, consent may be sought less than 24 hours after providing the study documentation. It must be recorded in the medical notes when the participant information sheet (PIS) has been given to the participant/legal representative.

The Investigator or designee will explain that participants are under no obligation to enter the trial and that they can withdraw at any time during the trial, without having to give a reason.

However, if the patient lacks capacity to give consent due to the severity of their medical condition (e.g. acute respiratory failure or need for immediate ventilation), then consent may be obtained from a relative acting as the patient’s personal legal representative. If there is no personal legal representative available (which due to restrictions of visitors to the hospital is likely) a professional legal representative (independent clinical responsible for the patients’ medical care or other person appointed by the hospital) will be asked to provide consent on behalf of the patient. Further consent will then be sought from a personal legal representative if one becomes available or from the patient if they recover sufficiently. If the patient refuses consent after recovery further assessments will be stopped.

In the event that a patient loses capacity as a result of treatment for their primary medical condition while on the study, an appropriate consultee will be sought as described above. No clinical trial procedures will be conducted prior to the participant/legal representative giving consent by signing the Consent form. Consent will not denote enrolment into trial.

A copy of the signed informed consent form will be given to the participant. The original signed form will be retained in the trial file at site and a copy placed in the medical notes.

The PIS and consent form will be reviewed and updated if necessary throughout the trial (e.g. where new safety information becomes available) and participants will be re-consented as appropriate.

### 6.4 Consent for historical standard of care controls (cohort 1 only)

Patients will be identified as historical controls by reviewing site admissions for cases that match treatment arm patients according to the characteristics listed in section 10.4.2. Historical controls can be identified from either site (i.e. Royal Free Hospital treatment arm patients can be matched with historical controls from Barnet Hospital). There is no limit to how far back in time the search for historical controls will go.

Initial collection of data will be done without patient consent under The Health Service (Control of Patient Information) Regulations 2002 and the notices issued by the secretary of state to healthcare

organisations, GP's, local authorities and arm's length bodies to allow sharing of information to support efforts against coronavirus (COVID-19).

These notices are currently due to end on 31 March 2021. Consent will not be sought from historical controls because the use of their personal identifiable information is covered by this notice.

The Royal Free trial team will retain a subject ID log that links the patient's trial identification number with their full name and hospital number. The log will indicate whether a patient is alive or dead at the time of enrolment. Because the both hospitals are part of the same Trust (Royal Free London NHS Trust), as per routine practice, the study team at the Royal Free Hospital also have access to the medical records of Barnet Hospital patients. The patient's identifiable information will not be recorded on the study database or case report forms, they will only be referred to by their unique trial ID number.

